7.2.5. Statistical Analyses / Methods

Details of the planned displays are provided in [Appendix 15](#): List of Data Displays and will be based on GSK data standards and statistical principles.

Unless otherwise specified, endpoints / variables defined in Section 7.2.1 will be summarised using descriptive statistics, graphically presented (where appropriate) and listed.

7.2.5.1. Statistical Methodology Specification

Key Secondary Statistical Analysis
Endpoint / Variables

 Proportion of participants with plasma HIV-RNA < 50 copies/mL at Month 12(OLI and BIK)/Month11(D2I) per Snapshot algorithm for the mITT-E population. Proportion of participants with plasma HIV-RNA < 50 copies/mL at Month 6(OLI and BIK)/Month 5(D2I) per Snapshot algorithm for the ITT-E population. Proportion of participants with plasma HIV-RNA ≥50 copies/mL at Month 6(OLI and BIK)/Month 5(D2I) per Snapshot algorithm for the ITT-E population.
Snapshot Dataset

 Virologic outcome (“HIV-RNA <50” or “≥50 c/mL”) per Snapshot algorithm is determined by the last available on-treatment HIV-1 RNA measurement within the analysis visit window of interest (please refer to analysis window defined in Section 16.3). In addition, participants who discontinue for reasons not related to adverse event with on-treatment HIV-1 RNA result at the time of discontinuation ≥50 c/mL or who change study treatment not permitted per protocol during Maintenance Phase before the analysis visit are classified as ‘HIV-RNA ≥50 c/mL’. Full details of the Snapshot algorithm are provided in Appendix 9: Snapshot Algorithm Details
Model Specification

 As specified in Section 7.1.5.1, with outcome being “HIV-1 RNA <50 c/mL” or “HIV-1 RNA ≥50 c/mL”
Model Results Presentation

 Adjusted CMH estimate of the difference in the proportion of participants with ‘HIV-1 RNA <50’ or with ‘HIV-1 RNA ≥50’ between two treatment groups (Q2M – BIK) and corresponding 95% confidence interval. Non-inferiority will be concluded if the lower bound of the two-sided 95% confidence interval (CI) for the CMH adjusted difference (Q2M – BIK) in proportion of participants with ‘HIV-1 RNA <50’ is greater than -12% at Month 12 (OLI and BIK)/Month 11 (D2I).
Subgroup Analyses

 Treatment Heterogeneity across randomization strata at Month 12 (OLI and BIK)/Month 11 (D2I) As specified in Section 7.1.5.1, with outcome being “HIV-1 RNA <50 c/mL” or “HIV-1 ≥50 c/mL”

Sensitivity and Supportive Analyses

- **Per-Protocol population analysis:**
To assess the impact of important protocol deviations, statistical analysis will be repeated using the Per-Protocol population and compared for consistency with the results from the primary ITT-E population analysis. Note for Month 12, PP population is based on the mITT-E population.
- **All Data as Observed:**
This analysis will include all observed data including those collected after confirmed pregnancy, in the ITT-E population. Note for Month 12, this analysis will be based on the mITT-E population.
- **Efficacy Sensitivity:**
This analysis will be based on the ITT-E population at Month 12.

CCI

CCI

CCI

8. SAFETY ANALYSES

The safety analyses will be based on the Safety population, unless otherwise specified. A “while on-treatment” strategy which considers data collected after confirmed pregnancy non-evaluable in the Q2M arm will be implemented for selected analysis including clinical laboratory, biomarker, and metabolic analysis. See [Appendix 13: Data Handling for Pregnant Subjects](#) for details. Note for safety-related reporting including adverse events and ECG, all observed data will be included.

8.1. Adverse Events Analyses

Adverse events analyses including the analysis of adverse events (AEs), Serious (SAEs) and other significant AEs will be based on GSK Core Data Standards. [Table 3](#) below provides an overview of the planned analyse with further details of data displays provided in [Appendix 15: List of Data Displays](#).

Table 3 Overview of Adverse Events Analyses

Endpoint	Absolute				Change from Maintenance Baseline					Max Post Maintenance Baseline				
	Summary		Individual		Stats Analysis	Summary		Individual		Summary		Individual		
	T	F	F	L		T	T	F	F	L	T	F	F	L
Exposure														
Extent of Exposure ^[1]	Y			Y ^[2]										
Adherence to Dosing Schedule ^[1]	Y													
Dosing Errors and IP Device Malfunctions				Y										
Injection Needle														
Length and Gauge	Y													
Adverse Events^[3]														
All AEs by SOC and PT	Y													
All AEs by SOC, PT and Toxicity	Y													
All Drug-Related AEs by SOC and PT	Y													
All Drug-Related AEs by SOC, PT and Toxicity	Y													
Common AEs by frequency ^[5]	Y	Y ^[6]												
Common Grade 2-5 AEs ^[5] by frequency	Y													

Endpoint	Absolute				Change from Maintenance Baseline					Max Post Maintenance Baseline			
	Summary		Individual		Stats Analysis	Summary		Individual		Summary		Individual	
	T	F	F	L	T	T	F	F	L	T	F	F	L
Drug-related Grade 2-5 AEs	Y												
All AEs				Y ⁽⁴⁾									
Serious and other significant adverse events													
All SAEs by SOC and PT	Y												
Reason for Considering as a Serious Adverse Event (FDA)				Y									
All Drug-Related SAEs by SOC and PT	Y												
Fatal SAEs				Y									
Non-Fatal SAEs	Y			Y									
Drug-related non-fatal SAEs	Y												
AEs Leading to Withdrawal/Permanent Discontinuation of IP	Y			Y									
Common Non-serious AEs by SOC and PT	Y												
Subjects and Number of occurrences of SAEs, Fatal SAEs, and Drug-related SAEs	Y												
AESI													
Depression, Suicidal and Self-Injury AEs by Prior History	Y												
AESI by SOC and PT	Y												
Characteristics of AESI	Y												
Syncope and Presyncope AE	Y												
Suicidality assessment													
PSRAE				Y ⁽⁷⁾									

Endpoint	Absolute				Change from Maintenance Baseline					Max Post Maintenance Baseline			
	Summary		Individual		Stats Analysis	Summary		Individual		Summary		Individual	
	T	F	F	L	T	T	F	F	L	T	F	F	L
Columbia suicidality (eC-SSRS)	Y												
Injection Site Reaction Adverse Events [12]													
ISR AEs (Event-Level) [17]	Y												
ISR AEs (Subject-Level) [18]	Y												
ISR AEs (Subject-Level) by Visit and Severity	Y	Y[19]											
Maximum ISR AE Grade by Needle Length [21]	Y												
Laboratory: Chemistry and Hematology													
Clinical Chemistry						Y				Y			
Lipids						Y							
NCEP shifts in lipids										Y[20]			
Hematology						Y				Y			
CCI													
Laboratory: Urinalysis (regardless of fasting status)													
Urine Dipstick	Y												
Urine Concentration						Y							
Proteinuria										Y[20]			
Laboratory: Hepatobiliary													
Liver Assessment				Y[14]									
Hepatobiliary Abnormality criteria	Y			Y									
Liver Chemistries				Y[11]						Y[20]			
Laboratory: Biomarkers													
Bone markers					Y	Y[10]							
Renal markers					Y	Y[10]							
CCI													
HOMA-IR, insulin and HbA1c					Y[16]	Y							
ECG													
ECG findings	Y			Y									

Endpoint	Absolute				Change from Maintenance Baseline					Max Post Maintenance Baseline				
	Summary		Individual		Stats Analysis	Summary		Individual			Summary		Individual	
	T	F	F	L	T	T	F	F	L	T	F	F	L	
ECG values				Y ^[22]		Y								
QTC values by Category	Y					Y								
Other														
Vital Signs (BP, HR, temp)				Y		Y								
Weight, Height and BMI	Y			Y		Y								
Waist Circumference and Hip Circumference	Y			Y		Y								
CCI														
Tanita Scale Assessments (Body Fat Percentage, Bone Mineral Mass, Muscle Mass, Total Body Water Percentage)	Y			Y		Y								
Abacavir HSR				Y ^[13]										
Participants who became Pregnant				Y										
Patient Profiles				Y ^[20]										
Metabolic Syndrome	Y		Y	Y		Y								
CCI														

NOTES:

- T = Table, F = Figures, L = Listings, Y = Yes display generated.
 - Stats Analysis = Displays related to any formal statistical analyses (i.e. modelling) conducted.
 - Summary = Represents TFL related to any summaries (i.e. descriptive statistics) of the observed raw data.
 - Individual = Represents FL related to any displays of individual participant observed raw data.
1. Refer to Section 16.6.2 and Section 16.6.4 for defining extent of exposure and adherence to dosing intervals.
 2. Includes reason for any dose change/interruption.
 3. For AEs reported more than once by a participant, the most severe intensity will be included. Separate summary tables including and excluding injection site adverse reactions.
 4. Listing of all AEs including verbatim text and preferred term, and listing of subject numbers for individual AEs.
 5. Common AEs are those with $\geq 5\%$ incidence in Q2M or BIK summarised by frequency.
 6. Plots of incidence rates and relative risk with 95% CI for Q2M vs.BIK.
 7. Four PSRAE listings: Event and Description (Section 1 and Section 2), Possible Cause (Section 3), Section 4 and Section 5 - Section 8.

8. Shift table summarising Maintenance Baseline (Day 1) vs. maximum Maintenance Phase result.
9. Scatter plot of baseline vs. maximum post-baseline for ALT and BILT. Scatter plot of maximum ALT vs. maximum Bilirubin.
10. Bone markers: Bone-specific alkaline phosphatase, procollagen type 1 N-propeptide, type 1 collagen cross-linked C-telopeptide, osteocalcin, 25 hydroxy-Vitamin D. Renal markers: Cystatin C; Beta-2-Microglobulin; Retinol Binding Protein (RBP). CCI
11. For subjects meeting hepatobiliary lab abnormality criteria.
12. Repeat for CAB/RPV, CAB, RPV respectively.
13. Separate listings for exposure to abacavir, history of drug allergies, family conditions, skin rash, symptoms, vital signs, individual symptoms and diagnostic category assignment. If no hypersensitivity to abacavir is observed, then only one blank listing will be provided for the exposure to abacavir.
14. Separate listings for event reporting, RUCAM score, biopsy, imaging, substance use and medical conditions. CCI
16. Statistical analysis will be performed for HOMA-IR.
17. Event-level summary: Percentages based on total number of ISR events including distribution of grade, duration, and event characteristics.
18. Subject-Level summary: Characteristics of ISR AE (Overall and by Common ISRs); Percentage based on number of participants; Includes distribution of grade and max grade, event characteristics, number of events per subject, rate of number of events per injection visit.
19. A corresponding plot for all grades and a separate plot for grade 3-5 events will be produced.
20. Patient profiles are not planned but can be produced post hoc, as necessary.
21. Please refer to Section 5.4 for derivation of needle length used in this summary.
22. For subjects with any value of potential clinical importance.

8.2. Adverse Events of Special Interest Analyses

Adverse events of special interest (AESI) are determined for CAB and/or RPV based on pre-clinical and clinical experience, along with information for the Integrase Inhibitor class of HIV medications and RPV safety profile. Table 4 shows the currently identified AESI, drug(s) of Interest and the reasons for inclusion. Changes to the MedDRA dictionary may occur between the start of the study and the time of reporting and/or emerging data from ongoing studies may highlight additional adverse events of special interest, therefore the list of terms to be used for each event of interest and the specific events of interest will be based on the safety review team (SRT) agreements in place at the time of reporting.

A summary by system organ class and preferred term will be provided for each of AESI. The characteristics of event occurrences during the maintenance phase will be summarized for AESIs. For Depression, anxiety and suicidal ideation/behaviour AESI, a summary by system organ class, maximum DAIDS toxicity grade and prior history of suicidal ideation will be provided.

The details of the current planned grouping, including Standardized MedDRA Query (SMQ) values (as applicable), and planned displays are provided in Appendix 11: Identification of Adverse Events of Special Interest (AESI) and Appendix 15: List of Data Displays.

Table 4 Adverse Events of Special Interest

Adverse Events of Special Interest	Drug(s) of Interest	Reason for Inclusion
Hepatic Safety Profile: Assessment of Risk of hepatotoxicity	CAB+RPV	Clinical, Class, Regulatory Interest, More prevalent in HIV population
Hyperglycemia	CAB	Class, Regulatory Interest
Hypersensitivity Reactions (HSR)	CAB	Class, Regulatory Interest, Occurs in HIV population
Rash	RPV	Class, Regulatory Interest, Occurs in HIV population
Prolongation of the Corrected QT Interval of the ECG in Supratherapeutic Doses	RPV	Non-clinical, Clinical, Regulatory Interest
Suicidal Ideation/Behaviour	CAB+RPV	Clinical, Class, Regulatory Interest, More prevalent in HIV population
Depression	CAB+RPV	Clinical, Class, Regulatory Interest, More prevalent in HIV population
Bipolar Disorder	CAB+RPV	Clinical, Class, Regulatory Interest, More prevalent in HIV population
Psychosis	CAB+RPV	Clinical, Class, Regulatory Interest, More prevalent in HIV population
Mood Disorders	CAB+RPV	Clinical, Class, Regulatory Interest
Anxiety	CAB+RPV	Clinical, Class, Regulatory Interest
Sleep Disorders	CAB+RPV	Clinical, Class, Regulatory Interest, More prevalent in HIV population
Injection Site Reactions (ISR) from Study Drug Injections [1]	CAB+RPV	Clinical
Seizures and Seizure-like Events	CAB	Clinical, Regulatory Interest
Weight Gain	CAB	Clinical, Class
Rhabdomyolysis	CAB	Clinical, Class
Pancreatitis	CAB	Clinical, Therapeutic Area, More prevalent in HIV population

Adverse Events of Special Interest	Drug(s) of Interest	Reason for Inclusion
Impact on Creatinine	CAB+RPV	Regulatory Interest, Therapeutic Area, More prevalent in HIV population
Safety in Pregnancy	CAB	Regulatory Interest, Class
NOTE: [1] A separate analysis will be performed for ISRs from study drug injections as described in Section 8.2.1		

8.2.1. Analyses for Injection Site Reaction Adverse Events

Injection Site Reaction (ISR) adverse events of interest are those from study drug injections. For the summary of ISR adverse events by visit and maximum severity (overall and by common ISRs): ISRs will be assigned based on onset date to the most recent planned IM injection visit prior or equal to the AE onset date.

Maximum grade at each visit will be derived as the maximum grade among ISRs assigned to the particular visit, with consideration for whether the summary applies to a particular preferred term (vs. across preferred terms), associated to CAB and/or RPV, or stratification by subgroup (such as needle length, refer to Section 5.4.2).

ISRs (based on investigator discretion) from study drug injections will be attributed to the causal agent (CAB vs. RPV) when this can be determined specifically based on the side of injection administration and the side of the reported ISR (as collected in the eCRF). If the causal agent cannot be determined in cases where both drugs are given on one side or the ISR is reported non-specifically, then the attribution to a specific causal agent will remain unknown.

Common ISR adverse events during the Maintenance Phase are defined by MedDRA preferred terms including injection site pain, injection site induration, injection site nodules and preferred terms of any other ISR with $\geq 5\%$ participants in the Q2M arm. The same set of common terms will be applied to ‘overall’ (CAB and/or RPV), CAB alone, RPV alone.

ISRs will be attributed to the needle length specifically based on the side of injection administration and the side of the reported ISR (as collected in the eCRF). If the needle length cannot be determined due to both drugs given on the same side with different needle lengths, then the attribution to a needle length will remain unknown.

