02*	
For Month 12 analysis only:
 
Participant has non-compliance with IP (including IM dosing errors) or took/received incorrect IP (i.e., other than the one to which they were randomized) up to an analysis timepoint of interest, meeting the following conditions during the Maintenance Phase:
 
 1. Two or more injection intervals affected by over dosage deviations, for example 
 • Extra injection or excessive volume administered • Length of time between injections less than 21 days between the first and second injections (between M1 and M2 for OLI; between Day 1 and M1 for D2I), or less than 52 days for all subsequent dosing intervals, excluding split doses up to the analysis visit of interest (M12 for OLI /M11 for D2I) 
* 21 = 28 – 7; 52 = 28 + 31 – 7 (smallest possible dosing interval allowed – 7 days)
 2. At least 10% of total time on-treatment with under dosing deviations in the Maintenance Phase up to the analysis visit of interest (i.e. Month 12 for OLI and BIK/Month11for D2I), where the % of non-compliance is calculated as: (total number of non-compliant dosing days / total number of intended exposure days) * 100%

Number	Exclusion Description

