Safety Follow Up Visit: Conduct approximately 4 weeks after the last dose of IP. Required only if the participant has ongoing AEs or lab abnormalities at the last on-study visit. This visit may be conducted by telephone.

Note: BP – Blood pressure, HR – Heart Rate, BMI – Body Mass Index, HDL – High Density Lipoprotein, LDL – Low Density Lipoprotein, PT - Prothrombin Time, PTT - Partial Thromboplastin Time, INR - International normalized ratio, PBMC – peripheral blood mononuclear cell, RNA – Ribonucleic acid, HbA1c = Glycated hemoglobin, HBsAg = hepatitis B surface antigen, HCV = hepatitis C virus, HIV-1 = human immunodeficiency virus type 1.

- a. Complete all Screening assessments within 35 days. Participants may begin the Maintenance Phase as soon as all Screening assessments are complete. Participants may be rescreened once and will be assigned a new participant number.
- b. For participants who elect to participate in the oral lead in period, oral CAB 30 mg + RPV 25 mg will be administered and the oral lead will start on Day 1. For participants who choose to go directly into injections, the first loading dose will be administered on Day 1. Visits for participants on the BIK arm are expected to occur every 56 days as projected according to the Day 1 visit. There is a ±3 day visit window, from the projected visit date (Maintenance Phase of the study).
- c. For participants who elect to participate in the oral lead in period, the first loading dose will be administered and the oral lead in will end. For participants who choose to go directly into injections, the second loading dose will be administered.
- d. Confirmation of eligibility to continue the Maintenance Phase, and eligibility to enter the Extension Phase.
- e. Collect full routine medical history plus (report at Baseline visit): HIV risk factors (may be collected at a later study visit), cardiovascular risk factors (assessments include smoking status and history, family history of cardiac events), recent [≤6 months] illicit drug use, intravenous drug use, gastrointestinal disease, metabolic, psychiatric, renal, bone, and neurologic disorders. At Month 11 (D21)/12 (OLI and BIK), assessments inclusive of smoking status, alcohol use and illicit drug use since the start of the study will be administered.

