	$(30^*m - 59) \leq \text{Injection Study Day} \leq (30^*m)$	$30^*m + 1$	$30^*m - 29$	Month 16, 18, etc.	Month m-1/m	Injection (m/2+1)
If subject permanently discontinued study treatment:						
	Subject received at least 1 injection of IP: Date > min(LTFU ART start date, max(Last Injection Date + 67, Date of Last Oral Dose + 1)) Subject received oral CAB/RPV only: Date > (Date of Last oral CAB/RPV Dose + 1)			Follow-up	Follow-up	Follow-up

NOTES:

- Analysis windows are applied after data has been assigned to the Maintenance Phase and Extension Phase as defined in Section 16.4.1
- Study day and injection study day is defined in Section 16.6.1
- Follow-up will be derived only for participants who permanently discontinued study treatment.
- Last oral dose may be CAB/RPV or SOC ART Oral Bridging where CAB/RPV is not available due to COVID-19 impact.
- Target Injection Study Day is only applicable to Q2M OLI subjects

[a] **Urinalysis:** All parameters provided by the central laboratory under the category of urinalysis.

[b] **Lipids:** Cholesterol, HDL Cholesterol Direct, LDL Cholesterol Calculation, LDL Cholesterol Direct, Total Cholesterol/HDL Cholesterol Ratio, Triglycerides

[c] **Bone Markers:** Bone-specific alkaline phosphatase, Procollagen type 1 N-propeptide, Type 1 collagen cross-linked C-telopeptide, Osteocalcin, 25 hydroxy-Vitamin D; **Renal Markers:** Cystatin C, Retinol Binding Protein, Beta-2-Microglobulin; **CCI**

[d] Analysis windows for parameters with sparse collection are noted.

16.3.2.2. Assessment Windows for Screening, Maintenance and Extension Phase Data – Q2M D2I Subjects

All Parameters except for where noted ^(c)	Analysis Window	Target Study Day	Analysis Timepoint 1	Analysis Timepoint 2	Notes
	Study Day ≤ 1	Study day of the earliest record	Screening	Screening	Screening
	Last available recorded value up to and including the date of first Maintenance Phase dose of IP	1	Maintenance Baseline (Day 1)	Maintenance Baseline (Day 1)	Injection 1
post-dose ECG	Value taken post-dose	1	Day 1 (Post Dose)	Day 1(Post Dose)	Injection 1
Urinalysis	$2 \leq \text{Study Day} \leq 60$	31	Month 1	Month 1	Injection 2
	$2 \leq \text{Study Day} \leq 72$				
	$61 \leq \text{Study Day} \leq 120$				
	$121 \leq \text{Study Day} \leq 180$	91	Month 3	Month 3/4	Injection 3

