
Timeliness of Injections relative to Date of Projected Dosing Visits are assessed by using "actual injection visit date - projected visit date from first injection". The injections of interest in adherence analysis are those after first injection. For participants who choose oral lead-in (Q2M OLI), the first injection is planned at Month 1. For Q2M D2I participants, the first injection is planned at Day 1. Each injection visit is counted only once. Individual CAB and RPV injections administered at the same visit are not counted twice. "Extra" unscheduled injections are excluded from all derivations. For example, if during a scheduled visit a participant receives 2 ml of injection instead of 3 ml due to a dosing error, but this participant returns one week later for the remaining 1 ml injection, then the additional visit is excluded. If a participant receives an extra injection at an unscheduled visit by mistake, this visit will also be excluded.
 
The categories of Timeliness of Injections relative to date of Projected Dosing Visits for summary are listed below:
 
 < -14 days -14 to - 8 days -7 to - 4 days -3 to -2 days -1 day 0 day 1 day 2 to 3 days 4 to 7 days 8 to 14 days >14 days Missed Injection without Oral Bridging Missed Injection with Oral Bridging Missed Injection with CAB+RPV Oral Bridging Missed Injection with SOC Oral Bridging

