16.15.8. Safety Figures

Safety: Figures					
No.	Population	GSK Standard / Example Shell	Title	Programming Notes	Deliverable [Priority]
Adverse Events					
3.1.	Safety	AE10	Plot of Common Maintenance Phase Adverse Events and Relative Risk(Excluding ISRs) – Q2M vs. BIK	207966/primary_15/F3.1	M6, M12
3.2.	Safety	mid201584/primary_07/T3.14	Plot of Incidence of Maintenance Phase Drug-Related Injection Site Reaction Adverse Events by Visit (Overall and Common)	Q2M only. 3 Sections: CAB and or RPV CAB RPV	M6, M12
3.3.	Safety	201584/primary_07/F3.17	Plot of Incidence of Grade 3-5 Maintenance Phase Drug-Related Injection Site Reaction Adverse Events by Visit (Overall and Common)	Q2M only. 3 Sections: CAB and or RPV CAB RPV	M6, M12
Laboratory					
3.4.	Safety	LIVER14	Scatter Plot of Maximum vs. Baseline for ALT and BILT – Maintenance Phase	GSK Statistical Display Standard Q2M and BIK	M6, M12
3.5.	Safety	LIVER9	Scatter Plot of Maximum ALT vs. Maximum Total Bilirubin– Maintenance Phase	GSK Statistical Display Standard Q2M and BIK. Remove the reference lines where ULN = 1X (only keep the 2X for BILT and 3X for ALT).	M6, M12

Safety: Figures					
No.	Population	GSK Standard / Example Shell	Title	Programming Notes	Deliverable [Priority]
3.6.	Safety	mid207966/primary_15/F3.18	Bar Chart of Fasting Lipid NCEP Categories	Baseline, M5/6 and M11/12. Include all 4 parameters: Triglycerides, Total Cholesterol, LDL, HDL	M6, M12
3.7.	Safety	mid215307/iss_01/F3.5	Bar Chart of Total Cholesterol/HDL Ratio Categories	Q2M and BIK . Baseline, M5/6 and M11/12. Keep big N as denominator	M6, M12
3.8.	Safety	mid215307/iss_01/F3.6	Bar Chart of Fasting Blood Glucose	Q2M and BIK . Baseline, M5/6 and M11/12 Keep big N as denominator	M6, M12
3.9.	Safety	207966/primary_15/F3.21	Plot of Incidence of Maintenance Phase Drug-Related Injection Site Reaction Adverse Events by Strata and Visit (Overall and Common) - CAB and/or RPV	Q2M only. Color-code Severity grade within each bar	M6, M12
3.10.	Safety	SAF_F1	Line Plot of Mean Change from Baseline by Visit for Bone, Renal, Inflammation and Insulin Resistance Markers		M12

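### The pooled Q2M injection-site-reaction plots by visit put OLI Injection 1 and D2I Injection 2 together at Month 1, so their points for the first two injections are not comparable

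*SAP*

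**What the plan says.** Section 8.2.1 of the SAP ties each ISR to an injection visit: "ISRs will be assigned based on onset date to the most recent planned IM injection visit prior or equal to the AE onset date".

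Section 16.15.8 lists three figures built on that assignment. Figure 3.2 is titled "Plot of Incidence of Maintenance Phase Drug-Related Injection Site Reaction Adverse Events by Visit (Overall and Common") and Figure 3.3 "Plot of Incidence of Grade 3-5 Maintenance Phase Drug-Related Injection Site Reaction Adverse Events by Visit (Overall and Common"). Figure 3.9 shows the same incidence by strata and visit. The programming notes for all three restrict them to the Q2M arm and mention no OLI or D2I sub-display. Tables 3.26 and 3.27 in Section 16.15.7, which give ISRs by visit and maximum severity, do list D2I and OLI columns beside the pooled Q2M column.

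The two paths start injections at different visits. Section 16.6.2 states: "For participants who choose oral lead-in (Q2M OLI), the first injection is planned at Month 1" and "For Q2M D2I participants, the first injection is planned at Day 1". Footnote c of Appendix 2 says of Month 1: "For participants who choose to go directly into injections, the second loading dose will be administered". The per-protocol rules in Section 16.1.1 place the interval from first to second injection "between M1 and M2 for OLI; between Day 1 and M1 for D2I".

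The window tables in Sections 16.3.2.1 and 16.3.2.2 carry two visit labels (Analysis Timepoint 1 and 2) and, in the Notes column, an injection number.

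**The concern.** A plot of ISR incidence over successive visits will usually be read as showing how tolerability changes with repeated injection. That reading needs each point to represent the same injection in everyone it covers. In the pooled Q2M figures the early points do not. The harmonised label does not help, because Analysis Timepoint 2 still reads plain Month 1 in both paths.

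OLI versus D2I is also the participant's choice (Section 2.3). Day 1 and Month 2 therefore each rest on a self-selected part of the arm, and differences among the first points combine injection order with choice of path.

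At stake is the picture for the first two injections of an adverse event of special interest that has its own analysis section. The SAP aligns the second injection elsewhere: the Perception of Injection questionnaire pairs OLI Month 2 with D2I Month 1 (Section 13.5.1.3 and Table 6), and injection delay in Section 16.6.3 is defined by injection order.

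**Working it through.** The SAP gives no figure of its own to reproduce here. The check has two steps.

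**Step 1. Map visit labels to injection numbers.** The inputs are the Notes columns of Sections 16.3.2.1 and 16.3.2.2. For later visits the tables give a general rule: for OLI at month m it is "Injection (m/2+1"), and for D2I it is (m+3)/2. Both rules also fit the earlier rows. OLI Month 4 gives 4/2 + 1 = 3 and Month 12 gives 12/2 + 1 = 7. D2I Month 3 gives (3+3)/2 = 3 and Month 11 gives (11+3)/2 = 7.

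| Visit label (Timepoint 2) | OLI injection | D2I injection |
|---|---|---|
| Day 1 | none | 1 |
| Month 1 | 1 | 2 |
| Month 2 | 2 | none |
| Month 3/4 | 3 | 3 |
| Month 5/6 | 4 | 4 |
| Month 7/8 | 5 | 5 |
| Month 9/10 | 6 | 6 |
| Month 11/12 | 7 | 7 |

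Of eight labels, one mixes injection numbers (Month 1), two hold a single path (Day 1, Month 2) and five are aligned. Under Analysis Timepoint 1 the first three labels are the same. Its later labels are odd months for D2I and even months for OLI, so Month 1 is again the only label that mixes injections.

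**Step 2. Illustrate the size.** The SAP gives neither ISR rates nor the D2I share. Assume incidence p1 = 70%, p2 = 50% and p3 = 40% after Injections 1, 2 and 3, the same in both paths, and a D2I share f of 25%, 50% or 75%.

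With participants injected at the visit as denominator:

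- Day 1 = p1 = 70%, Month 2 = p2 = 50%, Month 3/4 = p3 = 40%.
- Month 1 = (1 − f) × p1 + f × p2. For f = 25%: 0.75 × 70 + 0.25 × 50 = 65%. For f = 50%: 60%. For f = 75%: 55%.

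With all Q2M participants as denominator, Day 1 = f × p1 and Month 2 = (1 − f) × p2, while Month 1 and Month 3/4 stay as above:

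| D2I share | Day 1 | Month 1 | Month 2 | Month 3/4 |
|---|---|---|---|---|
| 25% | 17.5% | 65% | 37.5% | 40% |
| 50% | 35% | 60% | 25% | 40% |
| 75% | 52.5% | 55% | 12.5% | 40% |

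Under the first denominator the decline keeps its direction and is only stretched over an extra point. Under the second it becomes a rise, a fall and a partial recovery, although the assumed pattern is a steady fall. The SAP does not state the denominator for these plots. On an injection-number axis, with participants who received that injection as denominator, the values are 70%, 50% and 40% for any f, given the same profile in both paths.

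**The case against.** The strongest reply is that the month axis is an inference. The SAP does not say which label the plots use, injection-number labels exist in the window tables, and the layout rests on shells from other studies that are not in the document. This stands in part. A plot titled by visit is most naturally drawn on a visit label, but the SAP does not fix it. That is a reason to specify the axis.

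Second, Tables 3.26 and 3.27 already separate the paths. This stands. D2I Day 1 and OLI Month 1 together give the first injection for the whole arm. A reader might infer that the first-injection rate is unavailable, and the documents do not support that.

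Third, a reader might infer that the whole plotted trend departs from the injection sequence. It does not: from Month 3/4 to Month 11/12 the combined label and injection number coincide (Injections 3 to 7).

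Fourth, a reader might blame the assignment rule in Section 8.2.1. That rule works correctly within each participant; the gap lies in the figure specification.

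Finally, aligning by injection number pools first injections given after an oral lead-in with first injections given directly. This is a small real cost, and the separate OLI and D2I table columns still show the difference.

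**Conclusion.** The point holds within narrow limits. If Figures 3.2, 3.3 and 3.9 are drawn on the SAP's visit labels, their Day 1, Month 1 and Month 2 points for the pooled Q2M arm do not describe comparable injections, and Month 1 is the rate for neither Injection 1 nor Injection 2. Later injections are not affected when the combined label is used.

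The size cannot be taken from the document. Under the assumed rates, Month 1 lies 5 to 15 percentage points below the Injection 1 rate and 5 to 15 points above the Injection 2 rate. Distortion of the curve's shape arises only if all Q2M participants form the denominator, which the SAP neither states nor excludes.

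These are descriptive safety displays. No hypothesis test, margin or primary conclusion depends on them.

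**What to change.** In Section 16.15.8, specify for Figures 3.2, 3.3 and 3.9 that the horizontal axis is injection number 1 to 7, taken from the Notes column of Sections 16.3.2.1 and 16.3.2.2, or that OLI and D2I are drawn as separate series. In either case state the denominator as participants who received that injection. Section 8.2.1 needs no change. Tables 3.26 and 3.27 need none either, beyond optionally labelling the pooled Q2M column by injection number.

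The cost is a change of axis variable (or an added series) and a denominator statement in three figures. No new data are needed.
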